8.9.3.3 Spironolactone

Treatment groups will be compared for spironolactone duration, total dose and mean daily dose using ANCOVA models with baseline AOBP as a continuous covariate, and including factors for treatment group, baseline serum potassium (K^+ 4.3 to < 4.7 or 4.7 to 5.1 mEq/L), and history of Type 1 or 2 diabetes mellitus (Yes or No).

The number and percentage of subjects at each spironolactone dose will be presented by treatment group and visit. Dose at a visit is defined to be the investigator prescribed dose at that visit.

Time to discontinuation of spironolactone will be estimated using Kaplan-Meier methods, and will be compared between treatment groups using the log rank test.

8.9.3.4 Change in albuminuria (urine albumin to creatinine ratio [ACR]) from Baseline to Week 12 (ET)

Albuminuria will be summarized, by treatment group, at Baseline and Week 12, as well as change in albuminuria from Baseline to Week 12. The analysis will also be conducted for the subgroup of subjects whose ACR was elevated at baseline.

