4.1 Inclusion Criteria

Eligible subjects must meet all the following criteria:

1. Provide written informed consent prior to participation in the study
2. Age \geq 18 years
3. Taking at least three antihypertensive medications, one of which is a diuretic, for at least 28 days at a stable dose. ACE inhibitors or ARBs should be included among these three antihypertensive medications, unless previously not tolerated or contraindicated.
4. Uncontrolled hypertension as documented by AOBP SBP 135 to 160 mmHg at each Screening Visit; however, AOBP SBP may be $<$ 135 mmHg at either S2 or S3 Visits (see Section 7.3.2.2)
5. eGFR of 25 – \leq 45 mL/min/1.73 m² (mean [calculated by the IWRS] of two values measured at S1 and S3 or 7 to 28 days apart during the Screening/Run-in and calculated using CKD Epidemiology Collaboration [CKD-EPI] formula)
6. Qualifying local laboratory K⁺ measurements of 4.3 – 5.1 mEq/L obtained at Visits S1, S3 and S4 (all measurements must be within range)
7. Females of child-bearing potential must be non-lactating, must have a negative serum pregnancy test at screening, must use a medically acceptable form of birth control from 28 days prior to screening through the study and for 28 days after completion of the study

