Kaplan-Meier methods will be used to analyze the time to discontinuation of spironolactone. Treatment groups will be compared using the log-rank test.

Average daily dose and cumulative dose of spironolactone, and change in albuminuria (ACR) from Baseline to Week 12, will be analyzed using ANCOVA methods.

The EQ-5D-5L questionnaire results will be summarized at Baseline and Week 12/ET.

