3 RANDOMIZATION AND BLINDING

At Screening Visit 4, eligible subjects will be randomized 1:1 to spironolactone + patiromer or spironolactone + placebo. Randomization will be stratified by the Visit S4 locally measured potassium value (4.3 to < 4.7 mEq/L or 4.7 to 5.1 mEq/L) and by history of Type 1 or 2 diabetes mellitus (Yes or No).

To minimize the potential for bias, subjects, site personnel, and sponsor and vendor staff will remain blinded to treatment assignments, with the exception of unblinded staff required for the development of the final randomization schedule and for production of unblinded materials for the Data Safety Monitoring Committee (DSMC). Drug safety staff may also be unblinded where this is necessary to comply with regulatory requirements.

For production of DSMC materials, an unblinded sponsor biostatistician and unblinded sponsor programmer(s) will be identified.

The final randomization schedule will be produced by unblinded staff at Endpoint, the IWRS vendor for this study, and will be reviewed by the sponsor DSMC unblinded biostatistician.

The study will be unblinded after database lock.

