6.1.3 Other Efficacy Endpoints

The following other efficacy endpoints were specified by the protocol:

- Change in AOBP SBP from baseline to Week 12
- Potassium levels over time (measured both centrally and locally)
- Proportion of subjects with serum $K^+ \geq 5.5$ mEq/L
- Average daily dose and cumulative dose of spironolactone
- Time to discontinuation of spironolactone
- Change in albuminuria (urine albumin to creatinine ratio [ACR]) from baseline to Week 12
- EQ-5D-5L questionnaire results at Baseline and Week 12/ET

In addition to the endpoints specified in the protocol, the following additional endpoints will be examined:

- Change in AOBP SBP from baseline to Week 12 in the subgroup of patients remaining on spironolactone at Week 12
- Change in AOBP SBP/DBP over time

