8.9 Efficacy Analyses

8.9.1 Primary Efficacy Analysis

The primary efficacy endpoint for this study is the proportion of subjects remaining on spironolactone at Week 12.

A subject is defined as having remained on spironolactone until Week 12 if the End of Study Treatment eCRF confirms the subject has completed the full 12-week course of study treatment and the subject had not discontinued spironolactone early. Subjects who terminate from the study early or discontinue spironolactone early, for any reason, will be defined as not having remained on spironolactone until Week 12. The number and percentage of subjects remaining on spironolactone at Week 12, and the 95% CI, will be provided by treatment group. Confidence intervals will be obtained using the exact (Clopper-Pearson) method.

The percentage of subjects remaining on spironolactone at Week 12 will be compared between treatment groups (spironolactone + patiromer versus spironolactone + placebo) using a Cochran-Mantel-Haenszel (CMH) test, at α -level 0.05. The test will be stratified by baseline potassium category (4.3 to < 4.7 mEq/L or 4.7 to 5.1 mEq/L) and Type 1 or 2 diabetes mellitus (Yes or No).

The primary analysis will be performed using the ITT and PP Populations.

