8.9.4 Subgroups

The primary and secondary analyses will be performed for the following subgroups:

- Sex (male versus female)
- Age (< 65 versus \geq 65 years)
- Type 1 or Type 2 diabetes mellitus (presence versus absence at baseline)
- Baseline potassium category (4.3 to < 4.7 mEq/L versus 4.7 to 5.1 mEq/L) from central lab
- Region (Group A versus Group B)
- History of heart failure (presence versus absence at baseline)
- Baseline eGFR (< 30 versus \geq 30 mL/min/1.73 m²)

The test for interaction between treatment and a subgroup will be performed.

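### Free improvement (minor): the log-rank test for time to spironolactone discontinuation ignores both randomization strata, and the central-laboratory potassium subgroup has no category for values below 4.3 or above 5.1 mEq/L

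*SAP*

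**What the plan says.** **Stratification.** SAP section 3: "Randomization will be stratified by the Visit S4 locally measured potassium value" (cut at 4.7 mEq/L), and also by diabetes history. The primary CMH analysis follows this (SAP 8.9.1: "The test will be stratified by baseline potassium category", with diabetes added). The secondary ANCOVA (8.9.2), the Week 12 blood pressure models (8.9.3.1) and the ANCOVAs for spironolactone duration, total dose and mean daily dose (8.9.3.3) also include both factors.

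**Time to discontinuation.** "Time to discontinuation of spironolactone" is among the other efficacy endpoints (SAP 6.1.3). SAP 8.9.3.3 says it "will be compared between treatment groups using the log rank test"; Protocol 9.6.3 says "Treatment groups will be compared using the log-rank test". Neither names strata.

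**Potassium subgroup.** SAP 8.9.4 lists "Baseline potassium category (4.3 to < 4.7 mEq/L versus 4.7 to 5.1 mEq/L) from central lab" and adds "The test for interaction between treatment and a subgroup will be performed". The 4.3 to 5.1 mEq/L limits come from Protocol 4.1, inclusion criterion 6, which applies to local measurements "obtained at Visits S1, S3 and S4 (all measurements must be within range". Protocol 9.3 makes local values the basis for stratification. SAP 8.10.4 takes the central baseline as the last available central value up to first dose, with no range limit.

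**The concern.** **Log-rank test.** When randomization balances the arms within strata and the strata predict the outcome, a test that ignores them overstates the variance of the treatment comparison. It rejects too seldom under the null and loses some power under the alternative. The primary endpoint and this time-to-event analysis concern the same event, yet one is stratified and the other is not, and no reason is given.

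**Potassium subgroup.** Limits that screen local values have been carried over to a measurement they do not screen. Subjects with the lowest and highest central potassium can fall outside both categories, in the one subgroup meant to examine potassium. With no rule for them, their handling would have to be decided during analysis, possibly after unblinding.

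**Working it through.** **1. The plan's sample size.** SAP 2.3 gives N = 280 for 90% power to detect a 20-point difference at alpha 0.05 (two-sided, SAP 8.1). No control rate is given, so I take the largest-variance case, 40% versus 60% remaining:

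- n = [1.960·√(2·0.5·0.5) + 1.2816·√(0.4·0.6 + 0.6·0.4)]² / 0.2² = (1.3859 + 0.8879)² / 0.04 = 129.3, so 130 per arm.
- With continuity correction: (129.3/4)·[1 + √(1 + 4/(129.3·0.2))]² = 139.1, so 140 per arm, or 280.

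The stated figure is reproduced. Neither point below changes it.

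**2. Log-rank test with and without strata.** From the documents: 280 subjects, 1:1 allocation, two-sided 0.05, a 20-point difference and four strata (2 × 2). Assumed: four equal strata of 70, exponential times censored at Week 12, overall discontinuation rates held at the stated values, and hazard ratios (HRs) for the potassium and diabetes strata.

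The stratified statistic is Z = Σ(O_s − E_s)/√ΣV_s, with risk sets formed within stratum s. The unstratified statistic pools all risk sets.

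Hand check with no stratum effect, 60% versus 40% discontinued: treatment HR = ln(0.6)/ln(0.4) = 0.5108/0.9163 = 0.557. Expected events = 140·0.6 + 140·0.4 = 140. Power = Φ(|ln 0.557|·√(140/4) − 1.960), which is about Φ(1.50) = 93.3%. The simulation gives 93.2% unstratified and 93.1% stratified.

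Simulated rejection rates, 40,000 runs per cell (unstratified / stratified):

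| Potassium / diabetes HR | 60% v 40% discontinued | Loss (points) | 40% v 20% discontinued | Loss (points) | Null, 60% in both arms |
|---|---|---|---|---|---|
| 1.5 / 1.25 | 93.5 / 93.9% | 0.4 | 96.1 / 96.2% | 0.1 | 4.6 / 5.2% |
| 2 / 1.5 | 94.2 / 95.2% | 1.0 | 96.3 / 96.7% | 0.4 | 4.0 / 5.0% |
| 3 / 2 | 95.5 / 97.7% | 2.2 | 96.9 / 97.8% | 0.9 | 2.9 / 5.1% |

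Unequal strata (34/50/78/118) at 60% versus 40% give losses of 0.3, 1.0 and 1.9 points.

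The gain is larger where power is lower. A separate run (1,500 per cell) with a 15-point difference, 60% versus 75% remaining, gave 79.0 to 80.1%, 80.2 to 83.5% and 81.1 to 86.5% for HRs 2/1.41, 3/1.73 and 4/2.

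**3. Who falls outside the potassium categories.**

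- The entry limits bind local values at S1, S3 and S4 (Protocol 4.1).
- At S4 the central potassium sample goes for analysis only once eligibility is met (Protocol 6.1.4), so that result cannot act as an entry filter.
- The central baseline has no range limit (SAP 8.10.4).
- Protocol 9.7 lets a local value stand in for a missing central value, not for an out-of-range one.

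A central baseline of 4.2 or 5.2 mEq/L is therefore possible, and no rule places it.

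The share depends on figures the documents do not give. Assumed: true potassium normal with mean 4.7 and SD 0.25 to 0.30; within-person visit SD 0 to 0.20; central-minus-local difference unbiased, its variation split equally between the laboratories; values rounded to 0.1; all three local values within 4.3 to 5.1. One million subjects per cell:

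| SD of central-minus-local (mEq/L) | Share with no category | Of 280 (share × 280) |
|---|---|---|
| 0.05 | 0.5 to 1.9% | 1 to 5 |
| 0.10 | 1.4 to 3.9% | 4 to 11 |
| 0.15 | 2.6 to 6.1% | 7 to 17 |
| 0.20 | 4.4 to 8.8% | 12 to 25 |

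Moving the mean to 4.5 or 4.9 gives 0.9 to 9.3% over the same SDs (0.093 × 280 = 26). A cruder model spreads local values evenly over 4.3 to 5.1 and ignores the three-visit rule. It gives 8.5% at SD 0.10 and 26.4% at SD 0.30. I do not rely on it, because the rule removes many subjects near the limits.

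**The case against.** The first point can be called a preference. The unstratified log-rank test is valid, protocol and SAP agree on it, and no passage commits every analysis to the randomization strata. The endpoint is not primary or secondary, and stratified or adjusted views of the same question are already planned through the CMH test and the duration ANCOVA. At the design difference power is above 93% either way. The larger gains need hazard ratios for which the documents give no support: the Protocol Introduction links higher baseline potassium to hyperkalemia risk, in direction only, and gives no figure for diabetes. All of this stands, and it is why the point is an improvement and not an error. It does not supply a reason to leave the strata out.

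On the second point, the affected share is assumed, not known, and only one of seven subgroups is involved. That also stands. The gap in the definition does not depend on the share.

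The SAP's model descriptions do not say which laboratory supplies the potassium factor. I read it as the local stratum because Protocol 9.3 uses local values for stratification. SAP 7.1 keeps every ITT subject in the primary analysis.

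**Conclusion.** Both parts hold, at minor grade.

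The log-rank test omits the two factors the trial randomizes on. At the design difference the cost is about 0.1 to 2.2 points of power under the main set of assumed stratum hazard ratios, and nothing if the strata are not prognostic. The test errs on the conservative side.

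The potassium subgroup has a definite gap: subjects with a central baseline below 4.3 or above 5.1 mEq/L belong to neither category, and nothing elsewhere in the documents repairs this. Under the stated assumptions the share is about 0.5% to 9%; a larger central-local disagreement would raise it. Those subjects remain in the overall analyses and in the other six subgroups.

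Hazard ratios, stratum sizes, discontinuation rates, the potassium distribution and the laboratory SDs are all assumptions. The primary analysis and N = 280 are unaffected.

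**What to change.** - **SAP 8.9.3.3:** specify a log-rank test stratified by the randomization potassium stratum (local S4 value) and by history of Type 1 or 2 diabetes.
- **SAP 8.9.4:** make the central-laboratory categories open-ended, < 4.7 versus >= 4.7 mEq/L, or define the subgroup by the local randomization stratum. The same list already uses open-ended categories for age and for eGFR, although eGFR also has entry limits (25 to 45 mL/min/1.73 m²).

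The cost is two wording changes, made before unblinding. No new data are needed and the sample size stays the same.

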Determination of Sample Size:	This study will randomize approximately 290 subjects, to ensure that at least 280 subjects will be available for the primary analysis. This allows for the possibility that up to 10 subjects are randomized but never take study medication. A sample size of 280 subjects has 90% power to detect a difference between treatment groups of 20% or more in the proportion of subjects remaining on spironolactone at Week 12, at $\alpha = 0.05$.
Randomization:	Eligible subjects will be randomized 1:1 to either spironolactone + patiromer or spironolactone + placebo. The randomization will be stratified using the locally measured potassium at Visit S4 (4.3 to < 4.7 mEq/L or 4.7 to 5.1 mEq/L) and history of Type 1 or 2 diabetes mellitus (Yes or No).
Efficacy Analysis:	
Primary Efficacy Endpoint:	The proportion of subjects remaining on spironolactone at Week 12 will be compared between treatment groups (spironolactone/patiromer vs. spironolactone/placebo) using the Cochran-Mantel-Haenszel test, stratified by baseline serum potassium category (K^+ 4.3 – < 4.7 mEq/L or 4.7 – 5.1 mEq/L).
Secondary Endpoint:	AOBP SBP change from baseline to Week 12 or last available assessment prior to addition of any new BP medications or changes to any baseline BP medications will be analyzed using analysis of covariance (ANCOVA) methods.

Other Endpoints:	
Change in AOBP SBP at Week 12 will be analyzed using repeated measures as well as ANCOVA methods.
 
Average daily dose and cumulative dose of spironolactone, and change in albuminuria (ACR) from baseline to Week 12, will be compared between treatment groups using ANCOVA methods.
 
Kaplan-Meier methods will be used to analyze the time to discontinuation of spironolactone.
 
Potassium levels will be summarized for local and central values at each time point. Counts (%) of subjects who have experienced no potassium measurement ≥ 5.5 mEq/L will be presented at each time point.
 
The EQ-5D-5L questionnaire results will be summarized at Baseline and Week 12/ET.

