8.10.4.5 Spot Urine (ACR)

Spot urine will be collected for measuring ACR at Randomization/Baseline, Week 4, Week 8, and Week 12/ET. At Randomization/Baseline spot urine samples will be from 2 first morning voids, collected 1 and 2 days prior to the Randomization/Baseline Visit. At Weeks 4, 8, and 12, spot urine samples will be from 3 first morning voids collected on the day of the visit and on 1 and 2 days prior to the visit.

Mean values will be calculated for albumin and creatinine over the spot urine samples collected for each visit. The value of ACR at a visit will be the mean albumin value divided by the mean creatinine value.

Spot urine ACR will be summarized by treatment group with descriptive statistics at Randomization/Baseline, Week 4, Week 8, and Week 12. Note that change in ACR from Randomization/Baseline to Week 12/ET is an efficacy endpoint in this study (see Section 6.1.3).

A listing for spot urine results will be provided.

8.10.5 ***Vital Signs***

Blood pressure summaries have been described in Section 8.9.

Heart rate will be summarized, by treatment group, with descriptive statistics for each scheduled visit, and for the change from baseline to the corresponding time points.

Height is assessed only at S1 and will be summarized as part of the baseline characteristics.

Weight is assessed at S1, Randomization/Baseline, and at Week 12/ET. Weight will be summarized, by treatment group, with descriptive statistics for Randomization/Baseline and Week 12/ET, and for the change from baseline to Week 12/ET.

A listing for vital signs, weight and height will be provided.

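### The SAP replaces the protocol's between-arm ANCOVA of ACR change with summaries by group, leaving this endpoint without a treatment effect, confidence interval or test

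*SAP*

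**What the plan says.** The protocol makes the commitment twice. In the synopsis, under Other Endpoints of the statistical methods, "change in albuminuria (ACR) from baseline to Week 12, will be compared between treatment groups using ANCOVA methods". In section 9.6.3, "change in albuminuria (ACR) from Baseline to Week 12, will be analyzed using ANCOVA methods". Neither place names a scale or a covariate for ACR.

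SAP 8.9.3.4 has a different plan: "Albuminuria will be summarized, by treatment group, at Baseline and Week 12", and the change between those visits is to be summarized in the same way. It repeats this in subjects whose baseline ACR was elevated, without a cutoff. SAP 8.10.4.5 is also descriptive: "Spot urine ACR will be summarized by treatment group with descriptive statistics at Randomization/Baseline, Week 4, Week 8, and Week 12". Yet the same section notes that "change in ACR from Randomization/Baseline to Week 12/ET is an efficacy endpoint in this study".

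On scale, SAP 8.10.4.5 says "The value of ACR at a visit will be the mean albumin value divided by the mean creatinine value". SAP 8.1 sets the default summary for continuous variables: mean, SD, SE, median, quartiles and range. No log transformation, geometric mean or ratio to baseline appears in either document. Both documents (Protocol section 9, SAP section 1) let the SAP prevail where they differ.

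**The concern.** An efficacy endpoint for which the protocol named a comparison method has lost it in the controlling document. Two columns of summary statistics do not tell the reader how large the treatment difference is or how uncertain it is. If a comparison is wanted at reporting, its scale, covariates and handling of missing values would have to be chosen after unblinding.

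The scale is a separate and softer matter. ACR in chronic kidney disease can plausibly range widely, and SAP 8.9.3.4 itself expects subjects with and without elevated values. If the distribution has a long right tail, a few subjects with heavy albuminuria dominate the mean change. Restoring the protocol's ANCOVA without naming a scale would then bring back a test, but an inefficient one.

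**Working it through.** **1. What each 'other' endpoint was promised and what it kept.**

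| Endpoint | Protocol 9.6.3 | SAP |
|---|---|---|
| AOBP SBP change | ANCOVA and repeated measures | both kept (8.9.3.1) |
| Spironolactone dose | ANCOVA | kept in full (8.9.3.3) |
| Time to discontinuation | Kaplan-Meier, log-rank | both kept (8.9.3.3) |
| Potassium, EQ-5D-5L | summaries | summaries or listings (8.9.3.2, 8.9.3.5) |
| ACR change | ANCOVA | summaries only (8.9.3.4) |

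ACR is the only one that loses a named comparison method. Dose shares a protocol sentence with ACR, and for it the SAP says "Treatment groups will be compared for spironolactone duration, total dose and mean daily dose using ANCOVA models". This looks like an omission, though the documents do not say so.

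**2. The plan's own power figure.** The only one is for the primary endpoint: 280 subjects, 90% power, a 20-point difference. With assumed rates of 0.40 and 0.60 and two-sided alpha 0.05, the total is 260 without and 280 with continuity correction. It reproduces and is not in dispute. No power figure is given for ACR.

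**3. Log-scale ANCOVA, illustrative.** Assumptions, none from the documents: 120 evaluable per arm, true ratio 0.80, between-subject log SD B of 1.2 to 1.8, within-subject log SD W of 0.4 to 0.6.

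- Total variance V = B² + W²; correlation r = B²/V; residual SD s = √[V(1 − r²)].
- SE = s√(2/120); power ≈ Φ(|ln 0.80|/SE − 1.96), with |ln 0.80| = 0.223.
- B = 1.2, W = 0.4: V = 1.60, r = 0.90, s = 0.551, SE = 0.071; 0.223/0.071 = 3.13; power 88%.
- B = 1.8, W = 0.6: V = 3.60, r = 0.90, s = 0.827, SE = 0.107; 0.223/0.107 = 2.09; power 55%.

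Simulation of the same settings gives 55-87%, in agreement.

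**4. Raw-scale ANCOVA, same settings, by simulation.** About 11-40%; repeat runs move the ends of the range by up to about three points.

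**5. Dependence on skew.** A second simulation used 140 per arm and a true ratio of 0.80, with 3,000 runs per setting. Log SD is the SD of log ACR at a visit.

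| Log SD | Baseline-Week 12 correlation | Raw ANCOVA | Log ANCOVA |
|---|---|---|---|
| 0.5 | 0.70 | 99.7% | 99.9% |
| 1.0 | 0.70 | 48% | 77% |
| 1.0 | 0.85 | 67% | 95% |
| 1.5 | 0.70 | 14% | 40% |
| 1.5 | 0.85 | 21% | 65% |

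At log SD 0.5 the choice of scale does not matter. In the one null setting run (log SD 1.5, correlation 0.85), type I error was 4.0% for raw and 5.6% for log ANCOVA.

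**6. Dependence on the effect.** Both arms start spironolactone. Suppose ACR differs only because 20% more subjects stay on it. A between-arm ratio of 0.80 then needs ln 0.80/0.2 = −1.116 per such subject, a reduction of 1 − e^(−1.116) = 67%. With an assumed 30% reduction per such subject, the between-arm ratio is 0.70^0.2 = 0.931, about 7% lower. Log-ANCOVA power at 120 per arm is then only about 10-18%. This ignores dose differences and partial exposure.

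**The case against.** The strongest reply is that only the missing model is documented. The log scale is the reviewer's advice, the spread and the effect are assumed, and the endpoint is one of seven 'other' endpoints with no bearing on the primary or secondary result. All of that stands. The SAP's medians and quartiles will also show any skew, and its subgroup with elevated baseline ACR looks where an effect is most likely to appear. But neither gives a between-arm estimate with its uncertainty.

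A reader might infer more than the documents support in four ways:

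- **That the plan commits to a weak raw-scale test.** The SAP plans no test, and its raw scale is inferred from the definition of ACR and the absence of any transformation. An unadjusted t-test of raw change does worse still (about 8-34% in the settings of step 3), but neither document plans one. The fair comparator is raw-scale ANCOVA.
- **That the protocol promised a log analysis.** It names no scale.
- **That raw means are biased in direction.** Under randomization, the raw mean difference is unbiased for its own target. In the settings of step 3 it pointed the wrong way in about 7-28% of simulated trials, but that is sampling noise, a loss of precision.
- **That the fix would deliver 55-87% power.** Step 6 shows that it would not if the true difference is small.

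**Conclusion.** The concern holds as an undocumented departure. The controlling SAP removes a between-arm ANCOVA that the protocol names twice, and leaves ACR change without an adjusted effect, confidence interval or test. That conclusion needs no assumption.

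The preference for the log scale is a recommendation that rests on likely right skew. The power figures show the direction and possible size of the gain under assumed spreads and an assumed 20% reduction; they do not forecast this trial. The point is worth correcting, but its reach ends at this endpoint.

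**What to change.** In SAP 8.9.3.4, restore the comparison as an ANCOVA of log Week 12 ACR on log baseline ACR, treatment, baseline potassium stratum and diabetes. Report the geometric mean ratio with its 95% CI. Apply the same model in the elevated-baseline-ACR subgroup and state the cutoff. Add geometric means to the planned medians and quartiles. If the sponsor prefers description only, the SAP should say so and give the reason.

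The paragraph also needs a rule for missing and zero ACR, including whether an early-termination sample counts as Week 12. It should say which samples form the baseline covariate: Protocol 7.8 adds the 24-hour collection to the morning voids, while SAP 8.10.4.5 averages spot samples only.

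The cost is SAP wording and one extra model, with no new data. It should be settled before unblinding.
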